Title:

A Randomized, Controlled Clinical Trial Comparing the Use of High Purity Type-I Collagen-based Skin Substitute vs. Dehydrated Human Amnion/Chorion Membranein the Treatment of Diabetic Foot Ulcers

NCT Number:

NCT06470087

Date of the document:

31/10/2024

Title: A Randomized, Controlled Clinical Trial Comparing the Use of High Purity Type-I Collagen-based Skin Substitute vs. Dehydrated Human Amnion/Chorion Membrane in the Treatment of Diabetic Foot Ulcers

Introduction

Chronic wounds, especially diabetic foot ulcers (DFUs), place a significant financial strain on healthcare systems. In the United States, the estimated annual cost for treating these wounds is about \$30 billion. DFUs are the most prevalent form of lower extremity wounds, making up roughly 80% to 85% of such cases. Annually, between 6.5 and 7 million individuals in the U.S. are affected by chronic DFUs. With an aging population and increasing incidence of risk factors such as obesity and congestive heart failure, the prevalence of DFUs is expected to rise.

Chronic diabetic foot ulcers (DFUs) are linked to considerable suffering and a decline in quality of life, as the healing process is typically slow and painful. Even in optimal conditions, these ulcers can take weeks or months to recover, often experiencing a frustrating pattern of slow healing and repeated breakdown. Wound care specialists frequently encounter patients who have suffered from these ulcers for years, with some needing amputation as the only solution for pain relief.

Type-I collagen, when full, purified, and uncross-linked, offers 3,000 receptor sites per molecule for growth factors like fibroblasts to adhere to, making it an ideal matrix for wound healing. Type-I collagen shows 97% similarity across species, while Type-II and Type-III collagen only have 80% similarity within the same species. For instance, Type-I collagen in humans is quite similar to that in cows or birds. Furthermore, Type-I collagen is the least likely to provoke an immune response due to its lack of the sulfur-containing amino acid cysteine. In contrast, Type-II and Type-III collagen contain more cysteine, making them more immunogenic.

The objective of this study is to evaluate and compare the safety and effectiveness of High Purity Type-I Collagen-based Skin Substitute (HPTC) with Dehydrated Human Amnion/Chorion Membrane (dHACM) for treating diabetic foot ulcers (DFUs). This randomized, controlled clinical trial seeks to provide valuable insights into the best treatment strategy for enhancing healing outcomes and reducing the challenges posed by chronic DFUs.

Materials and Methods

Study will be carried out as a randomized, controlled open-label study to evaluate the safety and effectiveness of High Purity Type-I Collagen-based Skin Substitute (HPTC) compared to Dehydrated Human Amnion/Chorion Membrane (dHACM) for treating diabetic foot ulcers (DFUs). The trial will include patients with DFUs treated by wound care specialists at Adichunchanagiri Institute of Medical Sciences, B. G. Nagara, under the supervision of primary investigator [name] consent will be obtained from all participants prior to any study-related procedures, and each patient will sign an Institutional Ethics Committee/Investigational Review Board (IEC/IRB)-approved consent form. The investigator will comply with regulatory guidelines and Good Clinical Practice (GCP) in

obtaining and documenting informed consent. All study products will be produced, handled,

and stored in accordance with Good Manufacturing Practices (GMP). Strict patient confidentiality protocols will be maintained throughout the study.

Patient Screening and Eligibility

The study population will consist of patients seeking treatment for DFUs. Eligible patients will be those willing to participate and comply with scheduled visits on days 7, 10, 14, 17, 21, and 28. The study will include two phases: screening and treatment. The screening phase aimed to determine patient eligibility for the treatment phase. The inclusion and exclusion criteria are detailed in Table 1. During screening, a series of assessments will be conducted, including demographics, medical history, concomitant medications, vital signs, physical examination, leg ulcer history, clinical infection signs at the ulcer site.

Study Treatment:

The treatment phase of the study will commence with a series of evaluations to ensure patients remained eligible. Participants who will continue to meet the inclusion criteria after the screening phase will be randomly assigned to one of two groups:

- 1. Standard of Care (SOC) with High Purity Type-I Collagen-based Skin Substitute (HPTC).
- 2. Standard of Care (SOC) with Dehydrated Human Amnion/Chorion Membrane (dHACM).

Neither the patients nor the clinicians will be blinded to group assignments. The randomization will follow a balanced schedule, using permuted blocks of 12. When a patient will be ready for randomization, the study site will contact a representative from the sponsor, who will open a sequentially numbered opaque envelope to disclose the group assignment, maintaining allocation concealment.

Throughout the 4-week treatment phase, patients will be reassessed on days 7, 10, 14, 17, 21, and 28. The SOC dressing applied in both groups consisted of a three-layer system:

- First layer: Non-adherent, porous paraffin gauze.
- Second layer: Absorbent gauze pads.
- Third layer: Soft roll and Crepe bandage.

Note:

- a. 2 sizes of HPTC used:
- i. 0.8 in x 1.6 in or 2 cm x 4 cm (8 sq cm)
- ii. 1.6 in x 1.6 in or 4 cm x 4 cm (16 sq cm)
 - b. 2 sizes of dHACM used:
- i. 5 cm x 5 cm (25 sq cm)
- ii. 8 cm x 6 cm (48 sq cm)

If the study ulcer was found to be 100% re-epithelialized during the visit, no further study procedures will be conducted at that time. The patient will then be scheduled for a follow-up visit after one week to confirm the healing.

If full healing was not achieved, an evaluation will be carried out to check for any signs of clinical infection. If an infection is confirmed, treatment with topical antimicrobials or oral antibiotics will be permitted, though the use of topical antibiotics will be prohibited. After this infection assessment, the ulcer would be cleaned, photographed, and debrided at the investigator's discretion to ensure a clean and granulating wound base with minimal adherent slough. The Standard of Care (SOC) will be then re-applied, and patients will be instructed to keep the bandage dry. Additionally, they will be advised to contact or return to the study site if the bandage became soiled or removed.

Study Completion:

Patients will complete the study 4 weeks after their initial treatment visit. However, if a patient's study ulcer healed before the 4-week period, they will be considered to have completed the study at the time of full healing.

Complete healing will be defined as 100% re-epithelialization of the ulcer with no drainage. Throughout the study, patients will retain the right to decline participation or withdraw at any time without prejudice.

In the event of a patient's withdrawal, their last recorded wound measurement will be carried forward to determine the change in wound size and calculate their final outcome.

Study Outcomes:

Primary Endpoint:

• The primary outcome of the study will be the proportion of subjects who achieved improvement in wound healing, as observed on days 7, 10, 14, 17, 21, and 28. The wound closure of the target ulcer will be continuously monitored until the end of the 4-week period.

Secondary Endpoints:

- **Time to Achieve Complete Wound Closure:** Time taken for the target ulcer to achieve complete wound closure will be assessed on days 7, 10, 14, 17, 21, and 28.
- **Percentage Wound Area Reduction:** This will be measured weekly on days 7, 10, 14, 17, 21, and 28 using digital photography.
- **Mean Number of Repeated Applications of HPTC:** The average number of times the reapplication of High Purity Type-I Collagen-based Skin Substitute (HPTC) to achieve wound closure will be documented as part of the study process.

Exploratory Endpoint:

• The appearance, structural stability, and fragility of the newly formed skin will be documented at each visit. Any recurrence of the wound will also be monitored.

Subjects must be at least 18 years of age or older.	A subject known to have a life expectancy of less than 6 months.
Subjects must have a diagnosis of type 1 or 2 diabetes mellitus.	If the target ulcer is infected or if there is cellulitis in the surrounding skin.
At enrolment, subjects must have a target diabetic foot ulcer with a minimum surface area of 5.0 cm ² and a maximum surface area of 10.0 cm ² , measured post-debridement using a ruler.	Presence of osteomyelitis or exposed bone, probes to bone or joint capsule on investigator's exam, or radiographic evidence.
The target ulcer must have been present for a minimum of 4 weeks and a maximum of 52 weeks of standard care prior to the initial screening visit.	A subject that has an infection in the target ulcer that requires systemic antibiotic therapy.
The target ulcer must be located on the foot, with at least 50% of the ulcer below the malleolus.	A subject receiving immunosuppressants (including systemic corticosteroids at doses greater than 10 mg of prednisone per day or equivalent) or cytotoxic chemotherapy.
The target ulcer must be full thickness on the foot or ankle and must not probe to bone.	Topical application of steroids to the ulcer surface within one month of initial screening.
Adequate circulation to the affected foot as documented by any of the following methods performed within 3 months of the first screening visit: a. Transcutaneous Oxygen Measurement (TCOM) ≥ 30 mmHg b. Ankle-Brachial Index (ABI) between 0.7 and 1.3 c. Peripheral Vascular Resistance (PVR): Biphasic d. Toe-Brachial Index (TBI) > 0.6 e. Alternatively, arterial Doppler ultrasound can be performed to evaluate biphasic dorsalis pedis and posterior tibial vessels at the level of the ankle of the target extremity.	A subject with a previous partial amputation on the affected foot is excluded if the resulting deformity impedes proper offloading of the target ulcer.
If the subject has two or more ulcers, they must be separated by at least 2 cm. The largest ulcer satisfying the inclusion and exclusion criteria will be designated as the target ulcer.	A subject with a glycated hemoglobin (HbA1c) greater than or equal to 13%, taken at or within 3 months of the initial screening visit.

The subject must consent to using the prescribed off-loading method for the duration of the study.	A subject with a serum creatinine ≥ 3.0 mg/dL within 6 months of the initial screening visit.
The subject must agree to attend the twice-weekly/weekly study visits required by the protocol.	A subject with an acute Charcot foot, or an inactive Charcot foot, that impedes proper offloading of the target ulcer.
The subject must be willing and able to participate in the informed consent process.	Women who are pregnant or considering becoming pregnant within the next 6 months.
Patients must have read and signed the IEC/IRB-approved informed consent form (ICF) before screening procedures are undertaken.	A subject with end-stage renal disease requiring dialysis.
	A subject who participated in a clinical trial involving treatment with an investigational product within the previous 30 days.
	A subject who, in the opinion of the Investigator, has a medical or psychological condition that may interfere with study assessments.
	A subject treated with hyperbaric oxygen therapy or a Cellular and/or Tissue Product (CTP) in the 30 days prior to the initial screening visit.

Table 1: Inclusion and Exclusion Criteria

Statistical analysis:-

Descriptive statistics will be used to summarize the data. Quantitative data will be presented as means or medians, while qualitative data will be expressed as frequencies and percentages. The study aims to assess the proportion of study participants achieving wound healing by the end of the fourth week. To measure the proportion of participants showing improvement in wound healing, observations will be conducted on days 7, 10, 14, 17, 21, and 28. The proportion of participants achieving wound healing would be compared between both the groups using Chisquare/ Fisher's exact test. Additionally, the average reduction in ulcer size from baseline to the end of the fourth week will be compared between groups, and the significance of the reduction will be analysed using the independent t test/Mann-Whitney U test.

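### Comparing safety is a stated objective, but no safety endpoint, adverse-event collection or safety analysis is defined, and observation time depends on healing

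*Combined protocol and SAP*

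**What the plan says.** The objective paragraph of the Introduction commits the trial to "evaluate and compare the safety and effectiveness of High Purity Type-I Collagen-based Skin Substitute (HPTC" with dHACM. The opening of Materials and Methods repeats safety as something the study evaluates.

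Study Outcomes lists the following:
- Primary: "The primary outcome of the study will be the proportion of subjects who achieved improvement in wound healing".
- Secondary: time to closure ("Time taken for the target ulcer to achieve complete wound closure will be assessed on days 7, 10, 14, 17, 21, and 28"), percentage area reduction ("This will be measured weekly on days 7, 10, 14, 17, 21, and 28 using digital photography") and HPTC use ("The average number of times the reapplication of High Purity Type-I Collagen-based Skin Substitute (HPTC) to achieve wound closure will be documented").
- Exploratory: "The appearance, structural stability, and fragility of the newly formed skin will be documented at each visit", followed by "Any recurrence of the wound will also be monitored".

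Statistical analysis plans two between-group comparisons: the proportion healed and the mean reduction in ulcer size.

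Three places govern how long a patient is observed:
- Study Completion sets 4 weeks, but for patients who heal sooner "they will be considered to have completed the study at the time of full healing".
- Study Treatment stops study procedures at the visit where the ulcer is found closed, then schedules a visit one week later to confirm healing. The infection check applies only when the ulcer is not fully healed.
- The primary endpoint text says closure of the target ulcer is monitored through the end of the 4 weeks.

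**The concern.** The plan promises a safety comparison and then supplies nothing to make one with: no adverse-event definition, collection procedure, safety population, table or test. The mention of Good Clinical Practice in Materials and Methods concerns informed consent, so it does not fill the gap. For patients who withdraw, only the wound measurement is carried forward.

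The second problem is how any informally gathered events would arise. Both the length of observation and the infection check depend on whether the ulcer has healed, which is the effect under comparison. An arm that heals faster is watched for less time and checked for infection less often, so it would tend to show fewer events even if the products were equally safe. The trial is open label, so ad hoc reporting has no blinding to protect it.

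Recurrence is affected too. It can occur only after closure, when the completion rule treats the patient as finished, and the plan gives it no definition or time window.

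**Working it through.** **Step 1: objective against endpoints and tests.** There are one primary, three secondary and two exploratory items. The primary and the first two secondary items are efficacy. The third secondary item is product use in the HPTC arm only. The exploratory items (skin quality, recurrence) bear on safety but have no analysis. Both planned tests are efficacy tests. Safety outcomes with a planned comparison: none.

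**Step 2: size of the bias in crude percentages.** The documents give no closure rate, event rate or sample size, so there is no figure of the plan's own to reproduce. Every rate below is an assumption.

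Inputs:
- Closure by day 28: p = 60% v 40%, at a constant rate λ = −ln(1−p)/28, which gives 0.0327 and 0.0182 per day.
- Event hazard r: the same in both arms, and the same before and after healing. Two values: 0.01 per day (1 per 100 patient-days), and −ln(0.9)/28 = 0.00376 per day (10% risk over 28 days).
- Visits on days 7, 10, 14, 17, 21 and 28 (from the protocol).

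(a) Observation stops at the moment of healing:
- Mean time observed = p/λ: 0.6/0.0327 = 18.3 days and 0.4/0.0182 = 21.9 days.
- P(event seen) = r/(r+λ) × [1 − exp(−28(r+λ))]. With r = 0.01 this is 0.2341 × 0.6977 = 16.3% and 0.3541 × 0.5465 = 19.4%.

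(b) Healing is found at scheduled visits and observation stops there:
- P(event seen) = Σ P(healed between successive visits) × [1 − exp(−r × visit day)] + (1−p) × [1 − exp(−28r)].
- The interval healing probabilities are 0.2047, 0.0744, 0.0885, 0.0591, 0.0703, 0.1030 (60% arm) and 0.1199, 0.0469, 0.0586, 0.0413, 0.0516, 0.0817 (40% arm).

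(c) As (b), but the one-week visit counts: visit day is replaced by the smaller of visit day + 7 and 28.

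(d) Everyone is observed to day 28: 1 − exp(−28r).

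| Follow-up rule | Mean days, 60% v 40% arm | Events seen, r = 0.01/day | Gap (points) | Events seen, 10% 28-day risk | Gap (points) |
|---|---|---|---|---|---|
| (a) stops at healing | 18.3 v 21.9 | 16.3% v 19.4% | 3.0 | 6.6% v 7.9% | 1.3 |
| (b) stops at healing visit | 20.0 v 23.0 | 17.8% v 20.3% | 2.5 | 7.2% v 8.3% | 1.1 |
| (c) plus one-week visit | 23.5 v 25.2 | 20.8% v 22.2% | 1.4 | 8.4% v 9.0% | 0.6 |
| (d) all to day 28 | 28 v 28 | 24.4% v 24.4% | 0 | 10% v 10% | 0 |

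**Step 3: sensitivity to the healing contrast.** With 80% v 40% closure and the 10% event risk, rule (b) gives 5.9% v 8.3% (risk ratio 0.71) and rule (c) gives 7.6% v 9.0% (0.84). With 50% v 30% the risk ratios are 0.89 and 0.94. With equal closure rates the gap is zero under every rule.

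**Step 4: room to see recurrence.** If completion is at healing, the window after closure is nil. If the one-week visit counts, it is about 7 days. If everyone is seen at day 28, it is 28 minus the day of closure: 21 days for closure on day 7, and none for closure on day 28.

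**The case against.** Safety-relevant observations do exist. Infection signs are assessed at screening and at each visit where the ulcer is open, and skin fragility and recurrence are recorded. A reader might infer that the trial collects no safety information at all; the documents do not support that. What is missing is their definition, reporting and analysis as safety outcomes, and any collection of adverse events generally. That part of the criticism is untouched.

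A reader might also infer that patients simply leave at healing and that recurrence can never be seen. That rests on the completion sentence alone. The one-week visit offers one look at early breakdown, and the primary endpoint text speaks of monitoring through week 4. The documents conflict, and the conflict must be resolved. Counting the one-week visit reduces the gap from 2.5 to 1.4 points at the higher event rate but does not remove it, and no safety assessment is specified for that visit.

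The figures need two conditions. Healing speeds must differ, which is what the trial is testing. The event hazard must also be unchanged after closure. For target-ulcer infection the second is doubtful: if a closed ulcer is at lower risk, part of a lower count in the faster-healing arm is real benefit. This stands as a limit on the illustration. It also means that rates per patient-day would not be a safe remedy, since they correct for unequal observation only if the hazard is constant. Observing everyone to day 28 works in either case.

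Finally, one might want to state how large an event rate could be ruled out if no events were seen. No sample size is given, so no such bound can be calculated.

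**Conclusion.** The point holds. Safety is part of the stated objective, and the plan defines no safety endpoint, adverse-event collection or safety comparison; that conclusion needs no assumption. Followed as written, the plan cannot support a statement on comparative safety. Crude percentages of informally gathered events would tend to favour the arm that heals faster.

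The size of that distortion is illustrative only. At 60% v 40% closure with equal event hazards, it is about 0.6 points (10% 28-day risk, one-week visit counted) to 3 points (1 event per 100 patient-days, observation stopping at healing). It is larger for a wider healing difference and zero for none. The documents do not show that either product heals faster, so this is not a finding of bias toward HPTC or toward dHACM. The planned efficacy tests are not affected by this point, which is why the change is one the sponsor should make rather than one on which the trial depends.

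**What to change.** 1. Add a safety endpoint: patients with at least one adverse event, serious adverse event or confirmed target-ulcer infection, from first application to day 28.
2. Collect it in both arms at the existing visits, on the same form, whether or not the ulcer has closed.
3. Reconcile the completion rule, the one-week visit and the 4-week monitoring statement. Amend the completion rule so that every randomised patient, healed or not, has a day-28 safety and recurrence check. Define recurrence and state its window.
4. In Statistical analysis, report counts by arm with the risk difference and 95% CI in all treated patients.

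The cost is one adverse-event form, one table and a day-28 visit for early healers. Patients agree at entry to the scheduled visits, which include day 28, although the present completion rule may release early healers from it; the consent wording should match the amended rule. Patients who close near day 28 will still have almost no recurrence window, so recurrence should be reported descriptively, with the time observed after closure.

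### A single printed block size of 12 in an open-label, one-site trial makes about one assignment in seven predictable with certainty, so concealment is weakened near block ends

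*Combined protocol and SAP*

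**What the plan says.** All the relevant text is in the combined protocol and SAP. There are two arms, and the allocation rule under Study Treatment is: "The randomization will follow a balanced schedule, using permuted blocks of 12". Just before it the protocol states: "Neither the patients nor the clinicians will be blinded to group assignments".

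At the point of allocation, once the site has a patient to randomise, it calls the sponsor's designated person, "who will open a sequentially numbered opaque envelope to disclose the group assignment, maintaining allocation concealment".

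Materials and Methods describes one recruiting centre: "patients with DFUs treated by wound care specialists at Adichunchanagiri Institute of Medical Sciences". Most entries in Table 1 are measured thresholds, but one exclusion rests on judgement: "A subject who, in the opinion of the Investigator, has a medical or psychological condition that may interfere with study assessments". Ulcer area must be 5.0 to 10.0 cm², measured by ruler after debridement. Where a patient has several ulcers, the target is the largest one that meets the criteria.

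The document mentions no second block size, no stratification and no withholding of the block size from the site. It does not require enrolment to be fixed before the sponsor's representative is called.

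**The concern.** Concealment has two parts. The next envelope must not be readable, and the next assignment must not be deducible from those already made. The envelope procedure deals with the first. The second depends on the site being unable to reconstruct the list. Here the site sees every past assignment, there are no strata to complicate the count, and the protocol states the block length. Once six patients in a block have gone to one arm, the remaining assignments in that block are known.

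What is at stake is selection before randomisation. A recruiter who knows or suspects the next arm could defer a patient, judge one unsuitable, or read a borderline area as in or out of range. Such a patient leaves no trace among those randomised. The planned comparisons are unadjusted (chi-square or Fisher's exact test for healing, t test or Mann-Whitney for area reduction), so nothing planned would reveal or reduce the resulting difference between the arms.

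**Working it through.** **Inputs.** Block size 12, two arms, open label and one site are all stated. A 6:6 split is inferred from the word balanced, since no ratio is printed. A fixed block size is inferred from only one being given. The documents give no predictability figure and no sample size, so there is no figure of the plan's own to reproduce.

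**Assignments known with certainty.** For a 1:1 block of size 2m, the expected number made after one arm is used up is 2m/(m + 1). With m = 6 this is 12/7 = 1.71 per block, and 1.71/12 = 1/7 = 14.3%. Enumerating all C(12,6) = 924 possible blocks gives the same value and this distribution:

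| Certain assignments in the block | 1 | 2 | 3 | 4 | 5 | 6 |
|---|---|---|---|---|---|---|
| Share of blocks | 54.5% | 27.3% | 12.1% | 4.5% | 1.3% | 0.2% |

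The last assignment of every completed block is certain, and 100% − 54.5% = 45.5% of blocks give away two or more.

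**Best guess.** Always guessing the arm with more places left is right in [m + 2^(2m−1)/C(2m,m) − 0.5]/(2m) of assignments. With m = 6: 2048/924 = 2.216; (6 + 2.216 − 0.5)/12 = 7.716/12 = 64.3%, against 50% by chance.

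**Worst-case bias from certain slots.** Suppose a share f of slots is steered, with better-prognosis patients placed in one arm and worse-prognosis patients in the other, and let the two kinds differ by d in closure probability. The arm difference then shifts by f × d. With f = 0.143 and an assumed d of 10 to 20 points:
- 0.143 × 10 = 1.4 points
- 0.143 × 20 = 2.9 points

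If only a fraction of the certain slots is steered, the shift shrinks in proportion. The documents give no basis for d.

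**Alternatives.** These are worked at an assumed 60 patients. For varied blocks, the observer is assumed to know the set of sizes and to update after each assignment.

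| Scheme | Certain | Best guess right |
|---|---|---|
| Fixed blocks of 12 | 14.3% | 64.3% |
| Blocks of 8, 12 and 16 in random order | about 1.6% | 63.6% |
| Big stick, maximum imbalance 6 | 6.6% | 53.3% |

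Varied blocks remove nearly all certain knowledge but hardly change guessing. Big stick reduces both, but its mean final imbalance is about 3 patients, and about 17% of lists end 33 v 27.

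**The case against.** The strongest defence is that the protocol does more than many open-label trials. The sponsor's representative, not the site, opens numbered opaque envelopes, and only after the site calls. About 86% of assignments are never certain. A block of 12 is also less predictable than smaller fixed blocks: the certain share is 33.3% for size 4, 25% for size 6 and 20% for size 8. No open-label, single-site trial can hide its past assignments. All of this stands, and it limits how serious the point is. It does not explain why a single block size should be printed for the site to read.

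A reader might draw three stronger conclusions, and the documents do not support them.
- *The investigator can steer through the choice of target ulcer.* Table 1 removes that choice by taking the largest eligible ulcer. The debridement expressly left to the investigator's discretion takes place at follow-up visits, after assignment. The routes that remain are the investigator-opinion exclusion, the ruler measurement of post-debridement area and the timing of the call.
- *The bias could be 2.9 to 5.7 points.* This comes from steering on every guess: (2 × 0.643 − 1) = 0.286, multiplied by 10 to 20 points. It requires a patient of the wanted prognosis at every slot, as well as the assumed gap. It is an outer ceiling and not an expected effect.
- *No later analysis could remove the bias.* Adjustment for recorded baseline factors such as ulcer area and duration could remove the part that runs through them. Unmeasured prognosis would remain, and no adjustment is planned.

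**Conclusion.** The point holds as a cheap improvement. On the natural reading of the text (1:1, one fixed size, no strata), a site that keeps count knows on average one assignment in seven with certainty and can guess 64.3% correctly. The one-in-seven share is an average over completed blocks; an incomplete last block would change it slightly. If balanced did not mean 1:1, the share would differ: an 8:4 block, for example, gives 17.0%.

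The 1.4 to 2.9 points is a worst case. It rests on the assumed prognosis gap and on every certain slot being steered.

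A reader might infer that allocation concealment has failed, or that selection has taken place. The documents show neither. Envelopes held away from the site still protect most assignments from certain knowledge, and the text establishes only an opportunity, which requires someone to keep the tally and act on it.

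**What to change.** 1. Under Study Treatment, replace the reference to blocks of 12 with wording such as: *permuted blocks of randomly varied size, with sizes held in a document not available to the site*.
2. Generate the list from, for example, sizes 8, 12 and 16 in random order. The documents do not say whether enrolment has begun; if it has, apply this to the remaining assignments, since those already made stand.
3. Have the site log subject number, confirmed eligibility and post-debridement area before the sponsor's representative opens the envelope. This matters because varied blocks leave best-guess success near 64%, and a dated log makes a late change of mind visible.

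The cost is a new list, a one-sentence amendment and a short log, with the same envelopes and staff. The downside is that the arms may end slightly unequal: if recruitment stops inside a block of 16 the difference can reach 16/2 = 8, against 12/2 = 6 now.

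A big-stick list with maximum imbalance 6 is an optional alternative if guessing is the main worry. It gives up more of the balance that the protocol asks for.

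### The one-week visit meant to confirm healing has no stated effect on healed status: complete healing is defined at a single visit and early healers complete the study at that point

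*Combined protocol and SAP*

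**What the plan says.** The relevant statements are spread over four parts of the combined protocol and SAP.

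- **Study Treatment.** When the ulcer is found fully re-epithelialized at a visit, study procedures stop for that visit. "The patient will then be scheduled for a follow-up visit after one week to confirm the healing". Visits are listed for days 7, 10, 14, 17, 21 and 28. The trial is open-label: "Neither the patients nor the clinicians will be blinded to group assignments".
- **Study Completion.** The general rule is "Patients will complete the study 4 weeks after their initial treatment visit". For patients whose ulcer heals sooner, "they will be considered to have completed the study at the time of full healing". The definition is "Complete healing will be defined as 100% re-epithelialization of the ulcer with no drainage".
- **Study Outcomes.** The primary endpoint is worded as improvement in wound healing, and a second sentence there says closure of the target ulcer is monitored up to the end of the 4 weeks. For the secondary endpoint of time to closure, "Time taken for the target ulcer to achieve complete wound closure will be assessed on days 7, 10, 14, 17, 21, and 28". Under the exploratory endpoint, "Any recurrence of the wound will also be monitored".
- **Statistical analysis.** The proportion healed by week 4 is compared between groups with a chi-square or Fisher's exact test. Confirmation is not mentioned.

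**The concern.** A visit whose stated purpose is to confirm healing should be able to change whether the patient is counted as healed. Here nothing gives it that role. The definition is met at one visit, completion follows at once, and neither the analysis section nor the time-to-closure endpoint refers to the later visit.

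Three things are left to whoever analyses the data: whether a closure found open a week later is healed or not healed, what happens if the confirmation visit is missed, and which date is used for time to closure. In an open-label trial, where closure is judged by clinicians who know the allocation, those choices should not be made after results are visible. A single unconfirmed judgement is also more open to assessor bias than one that must hold a week later.

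The outcomes at stake are the week-4 healing proportion and time to closure. The primary endpoint as worded, improvement, need not be affected.

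**Working it through.** The plan gives no figure to reproduce on this point. The check is of visit timing and of what each passage does to healed status, followed by an illustration of size.

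**1. Timing.** Inputs are the listed visit days, the one-week interval to confirmation, and completion at full healing (or at 4 weeks). Confirmation day = day closure is first seen + 7.

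| Closure first seen | Study completed | Confirmation due | On the visit list? |
|---|---|---|---|
| 7 | 7 | 14 | yes |
| 10 | 10 | 17 | yes |
| 14 | 14 | 21 | yes |
| 17 | 17 | 24 | no |
| 21 | 21 | 28 | yes |
| 28 | 28 | 35 | no, after the 4-week end |

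For the five earlier days the early-completion rule applies, and completion comes 7 days before confirmation each time. Day 28 is a separate matter: that patient is not an early healer and completes under the general 4-week rule, but the confirmation visit falls a week beyond it.

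**2. Effect on healed status.** Take an ulcer closed without drainage on day 14 and open on day 21.

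- Definition: met on day 14.
- Completion rule: study completed on day 14.
- Confirmation visit: takes place on day 21, with no consequence stated.
- Monitoring of closure to week 4, and of recurrence: the re-opening may be recorded, but no rule changes the patient's status.
- Week-4 proportion and time to closure: no reference to confirmation.

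Read literally, the patient stays healed with a closure time of 14 days. Monitoring to week 4 also conflicts with completion on day 14.

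**3. Illustration of size.** All rates below are assumed. With apparent closure proportion p and re-opening share f at one week, confirmed healing = p × (1 − f).

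| p | f = 5% | f = 10% | f = 20% |
|---|---|---|---|
| 40% | 38% | 36% | 32% |
| 60% | 57% | 54% | 48% |
| 80% | 76% | 72% | 64% |

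Effect on the between-arm comparison:

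- Equal p and equal f: the difference is 0 on either definition.
- Unequal p, equal f: the difference is multiplied by (1 − f). For example, 60% v 40% with f = 10% gives 54% − 36% = 18 points instead of 20.
- Equal p, f = 5% v 20%: the difference moves by p × 0.15, which is 6 points at p = 40%, 9 at 60% and 12 at 80%.

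Missed confirmations: if a share m of closures is not seen again, counting them as healed or not healed moves the proportion by p × m. At p = 60% this is 3 points for m = 5% and 12 points for m = 20%.

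**The case against.** The best counter-argument is that completing the study is a disposition statement, not an outcome rule, and that the documents are simply silent on a failed confirmation. The primary endpoint text says closure is followed to the end of week 4. Closures first seen on days 7 to 21 have their confirmation on days 14 to 28, inside that window, so an analyst could class a re-opened ulcer as not healed at week 4. Much of this stands. A reader might infer that the plan states that a failed confirmation counts as healed; no passage says that. It follows only from the literal definition together with the absence of any other rule. But the monitoring and recurrence sentences contain no rule either, recurrence is exploratory only, and having two tenable readings is itself the defect.

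Full healing might be taken to mean confirmed healing. The only definition given has no confirmation element, and Study Treatment uses the same term for what is found at the visit itself.

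Single-visit closure, applied alike in both arms, can be a legitimate endpoint. If that is intended, the confirmation visit has no stated use in the outcome and the plan should say so.

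Three stronger readings are not supported:

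- A reader might infer that the withdrawal rule, under which "their last recorded wound measurement will be carried forward to determine the change in wound size and calculate their final outcome", locks in an unconfirmed closure. That rule applies to withdrawal, and a patient who has already completed cannot then withdraw. If the confirmation visit recorded an open ulcer, the last recorded measurement would be the open one.
- A reader might infer that failed confirmations are to be expected from the Introduction's account of ulcers breaking down repeatedly. That sentence concerns chronic ulcers in general and gives no rate for the week after closure.
- A reader might infer that one product is favoured. Nothing in the documents suggests that re-opening differs between arms.

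**Conclusion.** The point holds as an inconsistency in the outcome rule. The plan schedules a confirmation visit, defines healing without it, ends the study for early healers before it, and says elsewhere that closure is followed to week 4. Nothing reconciles these statements. On the literal definition, a closure that fails confirmation has already met the endpoint, though this is an inference and not an express statement. The day-35 confirmation of a day-28 closure is a second, separate gap.

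Size and direction are unknown, because the documents give no closure, timing or re-opening rates. The illustrative shifts of 6 to 12 points in the between-arm difference need an assumed re-opening contrast of 5% v 20%, which nothing in the documents supports. It should be fixed because it touches a tested comparison in an open-label trial and the remedy is cheap.

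**What to change.** Reconcile the completion, confirmation and monitoring statements with one outcome rule, identical in both arms:

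- (a) Count complete healing only if closure without drainage is still present at the one-week visit already planned, and date it to the visit at which closure was first seen.
- (b) Set study completion for a healer no earlier than that visit, and align the sentence on monitoring to week 4 with this.
- (c) Allow a closure first seen on day 28 to be confirmed on day 35 and counted as healed by week 4.
- (d) Count a failed confirmation as not healed at that date. A later closure counts only if first seen on a listed visit by day 28 and then confirmed. An ulcer first closed on day 21 and open on day 28, or first closed on day 28 and open on day 35, is therefore not healed.
- (e) State in advance that a missed confirmation counts as not healed, with the opposite assumption as a sensitivity analysis.
- (f) Report re-opening after a confirmed closure as recurrence. One consequence should be stated openly: an ulcer closed on day 7, confirmed on day 14 and open again by day 28 counts as healed with recurrence, while one closed on day 21 and open on day 28 does not count as healed.

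The cost is a short amendment to Study Treatment, Study Completion, Study Outcomes and Statistical analysis, and a possibly lower reported healing rate. Closures first seen on day 28 need up to one extra week, which the confirmation rule already implies.
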